6.15 Subject compensation

Participation in this trial is entirely voluntary. No cash compensation shall be provided for participants. However, subjects may be given parking vouchers for study-specific visits, in accordance with Lester & Sue Smith Breast Center clinical research standard operating procedures.

7. DRUG FORMULATION/STORAGE/SUPPLY

7.1 Vitamin D3, 5000 IU

Vitamin D3 at 5,000 IU strength is available over the counter at most retail pharmacies, and it will be supplied to patients through the study. They will be instructed to take 10 capsules one day each week, as described above in section 6.9.1, so that total dose is 50,000 IU weekly. The pills will be stored at controlled room temperature 15° to 30° C (59° to 86° F), in an appropriately labeled bin which is housed in a locked closet within the locked pharmacy.

7.2 Vitamin D3, 2000 IU

Vitamin D3 at 2000 IU strength is available over the counter at most retail pharmacies. The patients on the high dose arm will be provided with this medication for weeks 13-52 of the study. The pills will be stored at controlled room temperature 15° to 30° C (59° to 86° F), in an appropriately labeled bin which is housed in a locked closet within the locked pharmacy.

7.3 Caltrate-D, Calcium 600 mg & Vitamin D3 800 IU

The patients on the standard dose arm will be provided with this medication throughout the study. The pills will be stored at controlled room temperature 15° to 30° C (59° to 86° F), in an appropriately labeled bin which is housed in a locked closet within the locked pharmacy.

7.4 Drug Accountability

The investigator is responsible for accountability, reconciliation, and record maintenance of the study drugs (all doses of Vitamin D mentioned in sections 7.1-7.3). In accordance with all applicable regulatory requirements, the investigator or designated site staff must maintain investigational product accountability records throughout the course of the study. The responsible person(s) will document the amount of study drug supplied to and returned by patients.

8. DOSING DELAYS/DOSE MODIFICATIONS

8.1 Dose Modifications/Delays

For any patient in the study, if 25-hydroxyvitamin D level exceeds 120 ng/mL at any point, the patient will be taken off the study medication. If the 25 (OH)D level is >90 ng/mL, we will hold the vitamin D supplementation for 4 weeks, and then recheck vitamin D level. If it is <70 ng/mL after 4 weeks, the patient may resume vitamin D at 50,000 IU every other week if the patient was on the lead-in phase of the high dose arm. If the patient was on the continuation phase of the high dose arm, she would instead take 1000 IU/day. If the patient was on the standard dose arm, she would take Caltrate-D once every other day. If the 25-hydroxyvitamin D level did not fall to <70 ng/mL after 4 weeks of a drug holiday, then the vitamin D will be held for an additional 4 weeks. At the end of this 8 week period, patients will resume reduced vitamin D dosing as described above if the level has fallen to <70 ng/mL. However, if the level is still ≥70 ng/mL, then the patient will be taken off the study medication.

Similarly, if the calcium level is >11.0 mg/dL at any time during the study, the patient will be taken off the study. If the calcium level is between 10.5 and 11.0 mg/dL, the patient may follow the same vitamin D reduction schedule outlined above in which the vitamin D supplementation is held for 4 weeks, and may only be resumed at half dose if the calcium level is within normal limits, according to reference lab values. If the calcium level has not normalized after 8 weeks of drug holiday, then the patient will be taken off the study medication.

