6.12 Discontinuation of Treatment

In the event that study treatment is discontinued prematurely, subjects should undergo the study procedures as described in Section 6.5. NOTE: Subjects who discontinue study therapy will still be included in the overall evaluation of response (intent-to-treat analysis), regardless of the reason for therapy discontinuation. Study treatment may be discontinued for any of the following reasons.

- Breast cancer recurrence or new breast cancer
- Failure of the subject to attend the majority of scheduled visits. The protocol chair or her designee will determine when non-compliance with clinic visits should lead to removal from study.
- Lost to follow-up
- Withdrawal of consent.
- Unacceptable major toxicity, as determined by the treating investigator.
- Intercurrent illness or condition that would, in the judgment of the treating investigator, affect assessment of clinical status to a significant degree or require discontinuation of study treatment.
- At subject's own request. Note: The reason for discontinuation from the study must be documented.

- Study is closed for any reason (e.g. new information shows that the patient's welfare would be at risk if she continued study treatment).
- General or specific changes in the participant's condition which render the participant unacceptable for further treatment in the opinion of the treating investigator physician.
- 25-hydroxyvitamin D level exceeds 120 ng/mL at any point during the study
- 25-hydroxyvitamin D level is persistently >70 ng/mL, as outlined in [Section 8.1](#).
- Corrected calcium level >11.0 mg/dL on any measurement during the study, or corrected calcium level >10.5 mg/dL on three consecutive measures, as outlined in [Section 8.1](#).
- Symptomatic hypercalcemia which warrants discontinuation, at the discretion of the treating investigator physician, with symptoms including but not limited to confusion, lethargy, constipation, nausea/vomiting, abdominal pain, or muscle weakness.
- Development of symptomatic calcium-based renal stones

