6.14 Criteria for Removal from the Study

Participants will be removed from study when any of the criteria listed in Section 6.12 applies. All patients who are randomized in the study will be included in the overall evaluation of response (intent-to-treat analysis). All reasons for discontinuation of therapy should be documented clearly in the medical record.

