9.4 Toxicity Management

Calcium and 25-hydroxyvitamin D levels will be followed closely while the patients are on study to avoid hypervitaminosis D. Levels of 25-hydroxyvitamin D and calcium will be monitored and managed as outlined in [Section 8.1](#). For corrected calcium level greater than 11 g/dL, management will be according to standard of care and the judgment of the treating physician. It is recommended that the patient be hydrated with one liter of IV normal saline, and given one dose of pamidronate at 90 mg IV, if renal function is within normal limits. The use of calcitonin will be at the treating

physician's discretion. The patient will be followed closely and treated until the calcium level normalizes. The patient will not be re-challenged with the study medication in this case.

If the patient develops calcium kidney stones, she will also be taken off the study. She will be referred to her primary care physician and/or urology for further management of the kidney stones.

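### Sections 6.12, 8.1 and 9.4 state the calcium stopping rule inconsistently, so a woman's handling can depend on which section is read

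*Combined protocol and SAP*

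**What the plan says.** Four sections bear on what happens when calcium is high.

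- **Section 6.12** lists reasons for stopping treatment, introduced by "Study treatment may be discontinued for any of the following reasons". The first calcium criterion is "Corrected calcium level >11.0 mg/dL on any measurement during the study". The second is "corrected calcium level >10.5 mg/dL on three consecutive measures, as outlined in" Section 8.1.
- **Section 6.14** makes that list binding: "Participants will be removed from study when any of the criteria listed in Section 6.12 applies".
- **Section 8.1** gives the immediate stop as "if the calcium level is >11.0 mg/dL at any time during the study, the patient will be taken off the study". For 10.5 to 11.0 mg/dL it says the woman may follow the hold schedule: 4 weeks without vitamin D, then half dose only if calcium lies inside the laboratory's own reference range. It ends: "If the calcium level has not normalized after 8 weeks of drug holiday, then the patient will be taken off the study medication". The word corrected does not appear in 8.1, and neither does any rule based on three measurements.
- **Section 9.4** sends calcium monitoring and management to 8.1, then begins its treatment advice with "For corrected calcium level greater than 11 g/dL". It rules out re-challenge in that case.

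The baseline exclusion in Section 4.2.2 also uses corrected calcium. Calcium and albumin are listed as separate assays at every laboratory visit (Sections 6.1 to 6.5, Appendix B). No correction formula and no numerical laboratory limit are given. Section 3 allows up to 5 centers.

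**The concern.** Section 9.3 names hypercalcemia as the most common side effect of excess vitamin D, so this is the trial's main safety threshold. Section 6.12 attributes its repeated-value rule to Section 8.1, and a reader who follows the pointer finds a different rule. Sites could then act differently on the same results.

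Other parts of the plan depend on 8.1. Section 9.6.2 defines reportable laboratory abnormalities by it, and Section 8.2 ties disclosure of levels to its thresholds.

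The consequence of meeting the rule also varies. Above 11.0 mg/dL, 8.1 removes the woman from the study; after 8 weeks without normalization it removes her only from study medication. Section 6.12 is permissive and 6.14 is mandatory. This can reach the primary analysis, because Section 12.1.2 counts a woman who started medication and has no 12-week questionnaire as having developed arthralgia, and calcium is first checked on study at week 4.

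**Working it through.** There is no sample size or error rate to reproduce. The check applies the 6.12 and 8.1 rules to the same results.

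**Inputs from the documents.** Thresholds of 10.5 and 11.0 mg/dL (6.12, 8.1); rechecks after 4 and 8 weeks of hold (8.1); scheduled calcium at weeks 4, 12, 24, 36 and 52 (Appendix B).

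**Assumed, because the documents give no figure.** Laboratory upper limit L of 10.2 to 10.6 mg/dL. Correction formula: corrected = measured + k × (4.0 − albumin), with k from 0.6 to 1.0 mg/dL per g/dL.

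**1. End conditions, same calcium basis in both sections.** Take a trigger value and rechecks at 4 and 8 weeks, all at or below 11.0. Section 6.12's repeated-value criterion is met if all three exceed 10.5. Section 8.1 stops if both rechecks exceed L.

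| Values (mg/dL) | L | 6.12 calcium criterion | 8.1 |
|---|---|---|---|
| 10.8, 10.6, 10.6 | 10.6 | met | resume at half dose |
| 10.8, 10.6, 10.6 | 10.2, 10.3 or 10.5 | met | stop |
| 10.8, 10.4, 10.4 | 10.2 or 10.3 | not met | stop |
| 10.8, 10.4, 10.4 | 10.5 or 10.6 | not met | resume at half dose |

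The third row needs L below 10.4. With L exactly 10.5 and a trigger above 10.5, the two conditions coincide, and they agreed on every sequence tested. In the first row, 10.6 is both inside the laboratory range and inside 8.1's own hold band. Section 8.1 does not say which prevails, but neither reading of it stops the woman at that point.

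**2. Timing.** If the three measurements in 6.12 are scheduled visits, the interval from first to third is 24 − 4 = 20, 36 − 12 = 24 or 52 − 24 = 28 weeks. Section 8.1 decides at 8 weeks. If the 8.1 rechecks count as measurements, this difference goes.

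**3. Calcium basis, only if 8.1 is read as measured calcium.**
- Measured 10.8, albumin 3.5: corrected = 10.8 + k × 0.5, which is 11.1 (k = 0.6), 11.2 (k = 0.8) or 11.3 (k = 1.0). The 6.12 stop is met; 8.1 holds.
- Measured 11.1, albumin 4.5 (formula applied above 4.0 as well): corrected = 11.1 − k × 0.5, which is 10.8, 10.7 or 10.6. Section 8.1 removes her; the 6.12 criterion of more than 11.0 is not met.

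**4. Unit.** 11 g/dL is 11 × 1,000 = 11,000 mg/dL, a value that could never be met as printed.

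**The case against.** The strongest reply is that the sections can be read together. Wherever the protocol names a calcium basis it says corrected (4.2.2, 6.12, 9.4), both 6.12 and 9.4 point to 8.1, and albumin is scheduled with every calcium. On that view 8.1 uses shorthand. Its trigger value plus 4-week and 8-week rechecks make three measurements, which 6.12 may simply be summarizing, as its vitamin D criterion summarizes the matching rule in 8.1. Also, 6.12 is not an exclusive list. Where only 8.1 calls for a stop, stopping satisfies both sections.

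Much of this stands. A reader might infer that 8.1 deliberately uses uncorrected calcium; the text does not support that, because 8.1 is silent on the basis. A reader might also infer that the g/dL in 9.4 helps to split decisions. It does not: it is a slip in a management sentence that adds no rival end condition, and the bar on re-challenge agrees with stopping above 11.

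The reply does not remove the case in which 6.12 calls for a stop, 6.14 makes it mandatory, and 8.1 allows resumption. That case needs no view on the calcium basis, only a laboratory limit of 10.6. The summary reading works only if the laboratory limit is 10.5, which the protocol does not fix.

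On the analysis, Sections 6.12 and 6.14 keep all randomized women in the intention-to-treat evaluation, and early stoppers are due the Section 6.5 assessments, including the questionnaire. This limits the effect on the primary endpoint. Whether a questionnaire completed before week 12 would count as the 12-week one is not stated.

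**Conclusion.** The inconsistency is real. Three parts need no assumption: 6.12 attributes to 8.1 a rule that 8.1 does not contain, 8.1 does not state its calcium basis, and the stated consequence differs between 6.12, 6.14 and the two stops in 8.1. The unit in 9.4 is a typographical error.

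Different handling of the same woman is possible, not automatic. On one calcium basis it depends on a laboratory limit other than 10.5 mg/dL. On the 11.0 mg/dL threshold it depends on reading 8.1 as measured calcium and on an albumin value that moves the result across the line. It would go too far to say that the same woman is generally stopped under one section and continued under another. The documents give no frequency of borderline values, so the number affected is unknown and may be small. The point deserves correction because it concerns a safety threshold at up to 5 centers, not because a large effect on the results has been shown.

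**What to change.** Reconcile Sections 6.12, 6.14, 8.1 and 9.4 and state the calcium rule once, with the other sections pointing to it. The single statement should give:

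- one calcium basis, with the correction formula if it is corrected;
- one unit, with the g/dL in 9.4 corrected;
- one end condition for values of 10.5 to 11.0 mg/dL, including which measurements count and how a laboratory limit other than 10.5 is handled;
- one consequence for each criterion, separating the end of study medication from the end of study participation and saying whether it is mandatory.

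Which clinical rule applies is for the sponsor to decide. The cost is a wording amendment. No new sampling is needed to settle the basis, since albumin is already drawn with every scheduled calcium.

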3. STUDY DESIGN/SUMMARY

This is a randomized, multi-center, controlled, phase II study comparing high dose vitamin D vs. standard dose vitamin D for post-menopausal breast cancer patients who are beginning adjuvant aromatase inhibitor therapy. The study is intended to be conducted in up to 5 centers within the U.S.A which are routinely engaged in the administration of aromatase inhibitor therapy for the study specified population. All patients who are starting an AI in the adjuvant setting are eligible to participate in the study.

In order to preserve power and compensate for the interim futility analysis which tends to reduce power, the sample size of the study is increased from 88 per group to 93 per group, which is 186 total if considering a 5% drop out rate. A total of 186 patients at up to 5 centers will be randomized 1:1 to receive either 50,000 International Units (IU) oral vitamin D per week for 12 weeks followed by 2000 IU daily for 40 weeks, or 800 IU Vitamin D daily for 52 weeks. All women on both arms of the trial will also take calcium carbonate 600 mg daily.

The primary endpoint for this study is development of AIA in each arm after 12 weeks of AI therapy, as determined by patient questionnaires. Secondary endpoints include compliance with AI therapy, as well as correlation of low baseline vitamin D levels with development of AIA. Grip strength is an exploratory endpoint.

[figure not shown]
Throughout the 52 week study period, participating women will complete the questionnaire and grip strength measurement a total of three times in order to assess their arthralgia while on AI therapy. Compliance with aromatase inhibitor (AI) therapy will also be assessed throughout the

Vitamin D for AIA

study to determine if AI compliance is improved in women who are receiving Vitamin D. Additionally, women will also have periodic assessments of serum 25-hydroxyvitamin D to assess whether vitamin D levels correlate with AIA, and to ensure that calcium and 25(OH) D levels are within healthy ranges.

SCHEMA

High Dose vs. Standard Dose Vitamin D for Aromatase Inhibitor-Induced Arthralgia

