6.9.3 Caltrate-D

The patients who are randomized to the standard dose Vitamin D arm will take 1 Caltrate-D pill daily. Each pill contains 600 mg of Calcium and 800 IU of Vitamin D3. Patients will be instructed to take one pill daily, with food. Again, the medicine will be provided to them by the study, at no cost to the patient. Study personnel will instruct patients on how to take vitamin D, with the same instructions and precautions provided above, in [Section 6.9.1](#).

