6.9.4 Calcium, 600 mg

Patients on the high dose Vitamin D arm will be asked to take over-the-counter Calcium supplement, as is recommended as standard of care. This will not be supplied by the study, but patients will be instructed to take NatureMade Calcium 600 mg dietary supplement tablets – 1 tablet daily.

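### When calcium is 10.5 to 11.0 mg/dL, section 8.1 holds and halves only vitamin D, so calcium stops in the Caltrate-D arm while the high-dose arm's separate 600 mg calcium tablet stays instructed

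*Combined protocol and SAP*

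**What the plan says.** Section 8.1 sets the rule for moderately raised calcium: "If the calcium level is between 10.5 and 11.0 mg/dL, the patient may follow the same vitamin D reduction schedule outlined above". Under it, "the vitamin D supplementation is held for 4 weeks, and may only be resumed at half dose if the calcium level is within normal limits". The hold can be extended once: "If the calcium level has not normalized after 8 weeks of drug holiday, then the patient will be taken off the study medication".

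The half dose differs by arm and phase. In the high-dose arm it is 50,000 IU every other week in the first 12 weeks, or 1000 IU a day afterwards. For the other arm: "If the patient was on the standard dose arm, she would take Caltrate-D once every other day".

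Calcium reaches the two arms by different routes. Section 6.9.3 says of Caltrate-D: "Each pill contains 600 mg of Calcium and 800 IU of Vitamin D3". For the high-dose arm's calcium, section 6.9.4 says: "This will not be supplied by the study, but patients will be instructed to take NatureMade Calcium 600 mg dietary supplement tablets", one tablet a day. Section 3 gives the general instruction: "All women on both arms of the trial will also take calcium carbonate 600 mg daily".

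Section 6.12 lists, among the reasons to stop treatment, "corrected calcium level >10.5 mg/dL on three consecutive measures", and refers to 8.1 for the detail. On adherence, section 6.10 and the visit lists for weeks 12, 24 and 36 name the aromatase inhibitor and vitamin D. Calcium is first named in 6.5 (week 52 or early end of treatment).

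**The concern.** The rule was written around vitamin D, but its outcome turns on serum calcium. A woman restarts if her calcium is normal and comes off study medication if it is still raised after 8 weeks. Because Caltrate-D is a combined pill, holding vitamin D in the standard arm also removes supplemental calcium. In the high-dose arm the same words leave the calcium tablet in place. Followed literally, the protocol keeps a woman with raised calcium on calcium while her serum calcium is used to decide whether she may continue.

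Two things are at stake: a safety instruction that is weaker in one arm, and a restart-or-remove test applied under different calcium instructions in the two arms. The gap is in the arm given more vitamin D. Section 9.3 links hypercalcemia to excess vitamin D, so holds may be more frequent there, but the documents give no frequency.

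**Working it through.** The plan gives no figure to reproduce. The check sets the sections side by side and works out the calcium each arm is told to take.

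**Inputs**
- Standard arm: 600 mg calcium in each Caltrate-D pill, one a day (6.9.3).
- High-dose arm: one separate 600 mg tablet a day (6.9.4).
- Hold: 4 weeks, extendable to 8, or 28 to 56 days (8.1).
- Restart in the standard arm: every other day (8.1).
- Restart in the high-dose arm: vitamin D halved, calcium not mentioned (8.1).

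**Instructed calcium as written, with Caltrate-D not replaced during the hold**

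| Period | High-dose arm | Standard arm | Difference |
|---|---|---|---|
| Hold | 600 mg/day | 0 mg/day | 600 − 0 = 600 mg/day |
| After restart | 600 mg/day | 600 / 2 = 300 mg/day on average | 600 − 300 = 300 mg/day |

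Over the whole hold, the high-dose arm is told to take 600 × 28 = 16,800 mg (4 weeks) to 600 × 56 = 33,600 mg (8 weeks); the standard arm is told to take none.

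**Other reading.** A site could take section 3 to mean that a standard-arm woman buys separate calcium while Caltrate-D is held, and tops it up after restart. The differences are then 600 − 600 = 0 in both periods. Section 8.1 mentions no replacement, and 6.11 bars calcium beyond the study medications, so this end of the range is the weaker one. The ranges are 0 to 600 mg/day during the hold and 0 to 300 mg/day after it.

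**Does another section stop the tablet?**
- 9.4 refers back to 8.1; its extra measures apply only above 11.
- 7.4 defines the study drugs as the vitamin D products of 7.1 to 7.3. That includes Caltrate-D but not the separate tablet, so taking a woman off study medication does not clearly cover it.
- 6.9.4 and section 3 contain no exception for raised calcium.

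**Adherence.** Compliance is assessed at weeks 12, 24, 36 and 52, which is 4 visits. Calcium is named at 1 of the 4 (week 52), which for a completer is 52 − 12 = 40 weeks after the 50,000 IU phase. Week 4 has laboratory tests only and does not belong in this count. Serum calcium itself is tested at weeks 4, 12, 24, 36 and 52.

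**The case against.** The strongest reply is that this is silence, not an instruction to continue. Section 8.1 is permissive about the schedule. Under 8.2 the doctor may be told when a calcium threshold is crossed, and 6.9.4 treats the tablet as standard care, so a sensible physician would stop it. Section 6.11 can also be read as counting protocol calcium among the study medications, in which case a drug holiday might cover the tablet. And 9.3 names excess vitamin D as the cause, so holding vitamin D deals with the main driver.

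Much of this stands, and it keeps the point small. It does not close the gap. The written daily instruction is never suspended, 7.4 points away from the wider meaning of study medication, and with up to 5 centers individual judgment can differ.

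A reader might infer more than the documents support:
- That calcium use goes unrecorded until week 52. The review of concomitant medications at weeks 12, 24 and 36 may capture changes, and the compliance row in Appendix B names no product, so calcium can be recorded there. In the standard arm, Caltrate-D pill counts already measure it.
- That holds for 25(OH)D above 90 ng/mL raise the same problem. There the restart test is 25(OH)D, so with normal calcium the tablet matters much less.
- That 6.12 adds a second, independent removal rule. It refers to 8.1 and belongs to the same pathway.
- That the arthralgia comparison is biased. Women who stop treatment stay in the intention-to-treat analysis (6.12, 6.14), and no planned test compares serum calcium between arms.

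**Conclusion.** The point holds as a minor gap in a safety rule. For calcium of 10.5 to 11.0 mg/dL, the text of 8.1 stops and then halves calcium in the standard arm and leaves it unchanged in the high-dose arm, while serum calcium decides restart or removal. The differences of 600 mg/day during the hold and 300 mg/day after it rest on two assumptions: Caltrate-D is not replaced, and women follow the written instructions. A physician who stops the tablet removes the difference during the hold.

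The documents do not give the number of holds, actual calcium uptake, or the effect of 600 mg/day on serum calcium, so the clinical consequence cannot be sized. The adherence gap is missing detail and secondary. No effect on the arthralgia endpoint, alpha or sample size is claimed.

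**What to change.** Add one sentence to 8.1: for a hold triggered by calcium of 10.5 to 11.0 mg/dL, the high-dose arm's separate calcium tablet is held together with vitamin D and resumed every other day once calcium is normal. It should not apply to a hold for 25(OH)D above 90 ng/mL when calcium is normal. With Caltrate-D not replaced, both arms then get 0 mg/day during the hold and an average of 300 mg/day after restart.

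The cost is real but limited. A held high-dose woman has no supplemental calcium for 4 to 8 weeks and half the dose afterwards, possibly to week 52, while on an aromatase inhibitor. If the trigger came at the week 4 test and the hold lasted 4 weeks, the half dose could run for 52 − (4 + 4) = 44 weeks. The standard arm already bears the same under the current text.

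Optionally, name calcium in the existing compliance checks at weeks 12, 24 and 36 (6.3, 6.4 and 6.10), by count or direct question. This adds one question at three visits already planned. No study supply of the tablet, new visit or change to the analysis is needed.
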